10. STUDY MANAGEMENT BY ASTRAZENECA

10.1 Pre-study activities

Before the first patient is entered into the study, it is necessary for a representative of AstraZeneca to visit the investigational study site to:

- Determine the adequacy of the facilities
- Discuss with the investigator(s) (and other personnel involved with the study) their responsibilities with regard to protocol adherence, and the responsibilities of AstraZeneca or its representatives. This will be documented in a Clinical Study Agreement between AstraZeneca and the investigator
- Discuss where the identification of data will be recorded eg, pCRF, medical records and other associated documents. This will be documented in a Clinical Study Agreement
- Discuss the specific requirements of the genetic research with the investigator(s) (and other personnel involved with the study).

10.2 Training of study site personnel

Before the first patient is entered into the study, an AstraZeneca representative will review and discuss the requirements of the Clinical Study Protocol and related documents with the investigational staff and also train them in any study specific procedures and system(s) utilised.

The principal investigator will ensure that appropriate training relevant to the study is given to all of these staff, and that any new information relevant to the performance of this study is forwarded to the staff involved.

The principal investigator will maintain a record of all individuals involved in the study (medical, nursing and other staff).

10.3 Monitoring of the study

During the study, an AstraZeneca representative will have regular contacts with the study site, including visits to:

- Provide information and support to the investigator(s).
- Confirm that facilities remain acceptable.

- Confirm that the investigational team is adhering to the protocol, that data are being accurately and timely recorded in the CRFs, and that investigational product accountability checks are being performed.
- Perform source data verification (a comparison of the data in the CRFs with the patient's medical records at the hospital or practice, and other records relevant to the study) including verification of informed consent of participating patients. This will require direct access to all original records for each patient (eg, clinic charts).
- Ensure withdrawal of informed consent to the use of the patient's biological samples is reported and biological samples are identified and disposed/destroyed accordingly, and the action is documented, and reported to the patient.

The AstraZeneca representative will be available between visits if the investigator(s) or other staff at the centre needs information and advice about the study conduct.

10.3.1 Source data

Refer to Clinical Study Agreement for location of source data.

10.4 Study agreements

The principal investigator at each centre must comply with all the terms, conditions, and obligations of the Clinical Study Agreement for this study. In the event of any inconsistency between this Clinical Study Protocol and the Clinical Study Agreement, the Clinical Study Protocol shall prevail.

Agreements between AstraZeneca and the Principal Investigator must be in place before any study-related procedures can take place, or patients be enrolled.

10.5 Study timetable and end of study

The end of the entire study is defined as "the last visit of the last patient undergoing the trial".

The study is expected to start in quarter 2, 2008 and to be completed by quarter 4, 2008

The study may be terminated at individual centres if the study procedures are not being performed according to GCP, or if recruitment is slow. AstraZeneca may also terminate the entire study prematurely if concerns for safety arise within this study or in any other study with AZD9668.

11. DATA MANAGEMENT BY ASTRAZENECA OR DELEGATE

Data associated with biological samples will be transferred to laboratories internal or external to AstraZeneca.

Case Report Forms will be provided for the recording of data. The forms will be 3 level NCR (no carbon required) paper. Data are to be recorded legibly onto the case report forms in black or blue ballpoint ink. Corrections should be made legibly and initialled and dated by approved personnel; the reasons for significant changes must be provided. Correction fluid or covering labels must not be used. The top original, 1st and 2nd copy of each completed form will be collected. The top original and the 1st copy will be sent to data management personnel, the 2nd copy will be retained by the monitor. The 3rd copy will be retained at the investigator site.

The method of distribution of data queries will be documented in the study Data Management Plan (DMP). The original signed data query will be returned to data management personnel. The monitor will retain one copy and the other retained at the investigator site. On receipt of the data query by data management the database will be edited appropriately. It is not planned to raise any queries on patient completed data (including Bronkotest[®] diary card), however, full details of how this data should be entered into AMOS will be provided in the study Data Entry Instructions.

The CRF data will be verified against any source data before the pCRFs are collected from the study site by an AstraZeneca monitor, or AstraZeneca nominated monitor. The monitor will collect the original edited pCRF pages on an ongoing basis throughout the study, and return them to the relevant Local AstraZeneca Marketing Company (MC)/Clinical Research Region (CRR) or other agreed third party.

AstraZeneca R&D [REDACTED] will define the set-up of the AMOS database (modules, variables and dataset structures). The Local AstraZeneca MC/CRR or agreed third party will continuously enter data during the study into the AstraZeneca Monitoring System (AMOS) database held at AstraZeneca R&D [REDACTED]. No transfer of data will be required, as remote AMOS (RAMOS) will be used.

Electronic data checks will be used to validate the data entered into AMOS. Any missing, impossible, inconsistent or illegible entries in the pCRF will be referred back to the investigator via the monitor using Data Query Forms (DQFs) and responses returned to the Local AstraZeneca MC/CRR or third party responsible for data processing. If needed, the database will be updated accordingly.

Relevant study data will be coded using the most current version of the MedDRA and WHO Drug dictionaries, as outlined in the DMP, by the UK Coding Group (or agreed third party). If available, the global tool, GARNET, will be used to perform SAE reconciliation on an ongoing basis throughout the study, as outlined in the DMP, otherwise an alternative process will be defined within the DMP. Laboratory data will be electronically loaded into the database on an ongoing basis.

Prior to breaking the treatment codes, all decisions on the evaluability of the data from each individual patient must have been made and documented. The Study Delivery Team at AstraZeneca R&D [REDACTED] will document the date of clean file and database lock.

The Data Management Plan will describe the methods used to collect, check, process and quality control clinical data in greater detail. It will also clarify the roles and responsibilities of the various functions and personnel involved in the data management process.

In the case of genotypic data, only the date the patient gave consent to participation in the genetic research and the date the blood sample was taken from the patient will be recorded in the pCRF and database. The genotypic data will not be merged with the clinical dataset collected from the patient population for statistical analysis.

Genotype data generated in this study will be stored in the AstraZeneca genotyping LIMS database, or other appropriate secure system, separate from the database used for the main study.

Some or all of the clinical datasets from the main study may be merged with the genetic data in a suitable secure environment separate from the clinical database. The results from this genetic research will be reported separately from the clinical study report for the main study

12. EVALUATION AND CALCULATION OF VARIABLES BY ASTRAZENECA OR DELEGATE

12.1 Calculation or derivation of safety variable(s)

12.1.1 Safety variables

The following safety data will be collected: vital signs, ECG, haematology, clinical chemistry, urinalysis, sputum culture, reported adverse events. Change from baseline (Visit 2) to end of treatment will be calculated for relevant measurements.

12.1.2 Other significant adverse events (OAE)

During the evaluation of the AE data, an AstraZeneca medically qualified expert will review the list of AEs that were not reported as SAEs and DAEs. Based on the expert's judgement, significant adverse events of particular clinical importance may, after consultation with the Global Drug Safety Physician, be considered OAEs and reported as such in the Clinical Study Report.

Examples of these are marked haematological and other laboratory abnormalities, and certain events that lead to intervention (other than those already classified as serious) or significant additional treatment.

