Table 1	Primary outcome variables	20
Table 2	Secondary outcome variables	21
Table 3	Table of study assessments.....	25
Table 4	Spontaneous sputum sample summary.....	28
Table 5	Identity of investigational products	36

Table 6	Laboratory Parameters.....	45
Table 7	Bronkotest [®] Diary Card variables	48
Table 8	Volume of blood to be drawn from each patient	53

LIST OF FIGURES

Figure 1	Study design	23
----------	--------------------	----

LIST OF APPENDICES

Appendix A	Signatures (Not Applicable)
Appendix B	Additional Safety Information
Appendix C	IATA 6.2 Guidance document
Appendix D	Optional Genetic Research
Appendix E	St George’s Respiratory Questionnaire (SGRQ-C)
Appendix F	Bronkotest [®] Diary Card

LIST OF ABBREVIATIONS AND DEFINITION OF TERMS

The following abbreviations and special terms are used in this study protocol.

Abbreviation or special term	Explanation
AE	Adverse event (see definition in Section 7.3.1)
ALT	Alanine aminotransferase
AMOS	Astra Zeneca database
AST	Aspartate aminotransferase
ATC	Anatomical Therapeutic Chemical Classification of Drug
AUC	Area under the plasma concentration time curve from time zero to infinity
AUC ₍₀₋₂₄₎	AUC from time zero to 24 hours post-dose
AUC _{(0-24),ss}	AUC ₍₀₋₂₄₎ at steady state
AZ	AstraZeneca
BAL	Bronchoalveolar lavage
b.i.d	Twice daily dosing (latin)
CL/F	Apparent plasma clearance following oral drug administration
CL/F _{,ss}	CL/F at steady state
CL _R	Renal clearance
CL _{R,ss}	CL _R at steady state
C _{max}	Observed peak or maximum plasma concentration following drug administration
C _{max,ss}	C _{max} at steady state
CRR	Clinical Research Region
COPD	Chronic Obstructive Pulmonary Disease
CPK	Creatinine phosphokinase
CPMP	Committee for Proprietary Medicinal Products
CRF	Case report form
CRP	C-reactive protein
CSR	Clinical study report
CYP	Cytochrome P450
DAE	Discontinuation due to Adverse Event
DMP	Data management plan
DMPK	Drug metabolism and pharmacokinetics

Abbreviation or special term	Explanation
DNA	Deoxyribonucleic acid
DQF	Data query form
ECG	Electrocardiogram
Ecode	Enrolment code
EDTA	Ethylenediamine tetra-acetic acid
EU	European union
Fe ₍₀₋₄₈₎ (%)	Percentage of the dose excreted as unchanged parent in the urine from time zero to 48 hours
Fe _{(0-48),ss} (%)	Fe ₍₀₋₄₈₎ (%) at steady state
FEF25-75	forced expiratory flow between 25 and 75% of forced vital capacity
FEV ₁	Forced expiratory volume in the first second
FSH	Follicle-stimulating hormone
FVC	Forced vital capacity

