GARNET	Global application for reconciliation and narrative transcription
GCP	Good Clinical Practice
GGT	Gamma-glutamyltransferase
GMP	Good Medical Practice
GRand	Global randomisation system
hCG	Human chorionic gonadotropin
HELC	AstraZeneca Human Exposure Limits Committee
HIV	Human immunodeficiency virus
HRCT	High Resolution Computerised Tomography
IB	Investigator brochure
ICH	International Conference on Harmonisation
ICS	Inhaled corticosteroids
IL-1 β	Interleukin 1 beta
IL-6	Interleukin 6
IL-8	Interleukin 8
International Co-ordinating investigator	If a study is conducted in several countries the International Co-ordinating Investigator is the Investigator co-ordinating the investigators and/or activities internationally.
IP	Investigational product
LABA	Long-acting β agonists

Abbreviation or special term	Explanation
LAMA	Long-acting muscarinic antagonist
LDH	Lactate dehydrogenase
LFT	Liver function test(s)
LIMS	Laboratory information management system
LLN	Lower limit of normal
LLOQ	Lower Limit of Quantification
LTB ₄	Leukotriene B4
MAD	Multiple ascending dose
MC	Marketing Company
MCH	Mean cell haemoglobin
MCHC	Mean cell haemoglobin concentration
MCP-1	Monocyte chemoattractant protein
MCV	Mean cell volume
MedDRA	Medical Dictionary for Drug Regulatory Affairs
MID	Minimal clinically important difference
MUC5AC	Mucin 5AC
NCR	No carbon required
NE	Neutrophil Elastase
NOAEL	No observed adverse effect level
NOEL	No observed effect level
OAE	Other Significant Adverse Event (ie, adverse events of particular clinical importance, other than SAEs and those AEs leading to discontinuation of the patient from study treatment; see definition in Section 12.2.4
pCRF	Paper CRF
PD	Pharmacodynamic(s)
PEF	Peak Expiratory flow
PK	Pharmacokinetic(s)
PoP	Proof of principle
prn	Pro re nata (latin) – “As and when required”
PRO	Patient reported outcome
QT	ECG interval measured from the beginning of the Q wave (or the R wave if Q is missing) to the end of the T wave; the time interval of ventricular depolarisation and repolarisation

Abbreviation or special term	Explanation
QTc	Corrected QT
R&D	Research and development
RAMOS	Remote AMOS
RANTES	Regulated on activation, normal T cell expressed and secreted
RV	Residual Volume
SABA	Short-acting β agonists
SAD	Single ascending dose
SAE	Serious adverse event (see definition in Section 7.3.2).
SAMA	Short-acting muscarinic antagonist
SAP	Statistical analysis plan
S-CPK-MB	Serum creatinine phosphokinase, muscle and brain

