All AEs spontaneously reported by the patient or reported in response to the open question from the study personnel: “*Have you had any health problems since the last time you were asked*”, or revealed by observation will be collected and recorded in the CRF. When collecting AEs, the recording of diagnoses is preferred (when possible) to recording a list of signs and symptoms. However, if a diagnosis is known and there are other signs or symptoms that are not generally part of the diagnosis, the diagnosis and each sign or symptom will be recorded separately.

The investigator should review the diary card information to assess if any data constitutes an adverse event (see definition in Section 7.3.1) and should be recorded in the pCRF.

Adverse Events based on examinations and tests

Deterioration as compared to baseline in protocol-mandated laboratory values, vital signs and other safety variables will only be reported as AEs if they fulfil any of the SAE criteria or are the reason for discontinuation of treatment with the investigational product. If a deterioration in a laboratory value/vital sign is associated with clinical signs and symptoms, the sign/symptom will be reported as an AE and the associated laboratory result/vital sign will be considered as additional information. Any new or aggravated clinically relevant abnormal medical finding at a physical examination as compared with the baseline assessment will be reported as an AE.

Clinically relevant deterioration in non-protocol-mandated measurements will be reported as AE(s).

Wherever possible the reporting investigator uses the clinical, rather than the laboratory term (eg, anaemia versus low haemoglobin value).

Follow-up of unresolved adverse events

Any AEs that are unresolved at the patient’s last AE assessment in the study are followed up by the investigator for as long as medically indicated, but without further recording in the CRF. AstraZeneca retains the right to request additional information for any patient with ongoing AE(s)/SAE(s) at the end of the study, if judged necessary.

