7.3.5 Laboratory safety assessment

The laboratory parameters to be collected at the scheduled clinic visits are outlined in Table 6.

Blood samples will be analysed at a central laboratory.

Urinalysis will be performed locally at the study site.

The central laboratory will provide all the materials required for blood and urine sampling. Instructions for labeling, storage and shipping will be detailed in the laboratory manual. The central laboratory will also provide up to date reference ranges throughout the study for the management of patient safety.

Clinically relevant deviations from the reference range in the lab values will be handled as outlined in Section 7.3.3.

For blood volumes see Section 8.1.

Table 6 Laboratory Parameters

Haematology (Blood)	Clinical Chemistry (Serum)	Urinalysis (Urine)
Haemoglobin	Creatinine	Protein
Erythrocyte count	Total bilirubin ^d	Glucose
Haematocrit	Alkaline phosphatase	Haemoglobin
Mean Cell Volume (MCV)	Aspartate aminotransferase (AST)	
Mean Cell Haemoglobin (MCH)	Alanine aminotransferase (ALT)	
Mean Cell Haemoglobin Concentration (MCHC)	Albumin	
Platelet count	Potassium	
Leucocyte count (absolute and percentage including Neutrophil, lymphocyte, monocyte, eosinophil and basophil counts)	Calcium, total	
Reticulocyte count	Sodium	
	Cholesterol	
	Triglycerides	
	Urea	
	Gamma Glutamyltransferase (GGT)	
	Creatinine phosphokinase (CPK) ^a	
	Lactate dehydrogenase (LDH)	
	Glucose	
	Free thyroxine (T4) ^b	
	Thyroid stimulating hormone (TSH) ^b	
	Haptoglobin	
	Follicle stimulating hormone (FSH) ^c	
	hCG ^c	

^a If elevated, S-CPK-MB will be analysed (will not be databased)

^b Included at Visit 1 only

^c Included at Visit 1 for female patients only

^d If elevated, unconjugated bilirubin will be analysed (will not be databased)

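### Section 12.1.2 looks for laboratory OAEs in a list that, under Section 7.3.3, cannot contain an asymptomatic, non-serious scheduled abnormality that does not stop treatment

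*Protocol*

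**What the plan says.** Protocol Section 12.1.2 sets out how OAEs are identified. While the AE data are being evaluated, "an AstraZeneca medically qualified expert will review the list of AEs that were not reported as SAEs and DAEs", and events judged clinically important may be reported as OAEs. On what the review is meant to find, it says: "Examples of these are marked haematological and other laboratory abnormalities". The second kind of example is events that led to intervention or significant additional treatment. The abbreviation list defines the category with the same exclusion: "other than SAEs and those AEs leading to discontinuation of the patient from study treatment".

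Section 7.3.3 decides what enters the AE list. A deterioration from baseline in a protocol-mandated safety measurement "will only be reported as AEs if they fulfil any of the SAE criteria or are the reason for discontinuation of treatment". If it comes with signs or symptoms, the sign or symptom is the AE and the measurement is supporting information. Clinically relevant deterioration in measurements the protocol does not mandate is an AE without that condition, and so is a new or aggravated clinically relevant finding on physical examination.

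Section 7.3.5 adds no other route for laboratory results: "Clinically relevant deviations from the reference range in the lab values will be handled as outlined in Section 7.3.3".

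**The concern.** The two rules were written for different purposes and do not fit together. Section 7.3.3 keeps routine test results off the AE list unless they are serious or stop treatment. Section 12.1.2 then searches the AE list, less exactly those two kinds of event, for marked test results. For one class of finding the search has nothing to search.

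That class matters in this trial. Section 2.1 reports minor haematological abnormalities and slight QT prolongation at a high dose in a 28-day dog study. Section 2.4 gives continued haematological and biochemical monitoring, including for haemolysis, as the mitigation. Safety and tolerability is a secondary objective (Section 3.2). If the study report says that no laboratory OAEs were identified, a reader will take it that a medical expert looked at the laboratory findings and judged none important. Under the rules as written, the expert need not have been shown them.

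**Working it through.** No arithmetic underlies the main point. It follows from setting the rules side by side.

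**Step 1: the review list.** By Section 12.1.2, the OAE list is the reported AEs minus SAEs minus DAEs. The abbreviation list expands DAE as "Discontinuation due to Adverse Event".

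**Step 2: entry to the AE list.** By Section 7.3.3 a scheduled result becomes an AE by one of two conditions: it meets an SAE criterion, or it is the reason for stopping study treatment. The first produces an SAE and the second a DAE. ECG is not named in that sentence. It is included here by inference, because the sentence extends to other safety variables and Section 12.1.1 lists ECG among the safety data.

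**Step 3: combine them.**

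| Finding | AE under 7.3.3? | On the 12.1.2 list? |
|---|---|---|
| Scheduled result meeting an SAE criterion | Yes, as an SAE | No, removed |
| Scheduled result that is the reason for stopping | Yes, as a DAE | No, removed |
| Scheduled result with signs or symptoms, not serious, treatment continues | The sign or symptom is the AE | Yes, through the symptom |
| Scheduled result, asymptomatic, not serious, treatment not stopped for it | No | No |
| Clinically relevant deterioration in a non-mandated measurement | Yes | Yes, unless SAE or DAE |
| New or aggravated clinically relevant physical-examination finding | Yes | Yes, unless SAE or DAE |

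Rows 1 and 2 are reported elsewhere, so nothing is lost there. Row 4 is the gap.

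**Step 4: timing.** Section 6.4.2 has the last dose taken in the clinic at Visit 4. Table 3 schedules safety bloods at Visits 1, 2, 2a, 3, 4 and 5, which agrees with the six haematology samples in Table 8. Visit 2 bloods are pre-dose, so four draws follow the first dose: 2a, 3, 4 and 5.

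- A Visit 5 result comes after dosing has ended and cannot be a reason for stopping. It can become an AE in its own right only by meeting an SAE criterion, however marked it is.
- Visit 4 bloods are taken pre-dose and analysed centrally (Section 7.3.5). If the result returns after that day's dose, which the protocol does not state, the same applies.
- Vital signs and ECG at Visit 4 are also taken 1–2 hours after the last dose, so those readings are in the same position as Visit 5.

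For 40 completing patients the post-first-dose draws number 4 × 40 = 160. The discontinuation condition is closed for 1 × 40 = 40 of them (25%), or for 2 × 40 = 80 (50%) if Visit 4 results return after the last dose. These are counts of blood draws, not of expected abnormalities.

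**Step 5: what remains in the report.** Laboratory data are loaded electronically (Section 11). Change from Visit 2 to end of treatment is calculated for relevant measurements (Section 12.1.1). All data are listed, and summarised and plotted as appropriate (Section 13.2). Three items are thinner. Unconjugated bilirubin and S-CPK-MB are not databased (Table 6, notes d and a), and for ECG the pCRF holds only the investigator's overall evaluation (Section 7.3.7).

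**The case against.** The strongest objection is that this is a missing label and not missing data. A marked platelet fall would still appear in the laboratory listings, the AE-reporting threshold in Section 7.3.3 is deliberate, and OAE classification is a descriptive step in an exploratory 40-patient study. Most of this stands. It limits the point to classification and medical review. It does not remove the mismatch, because Section 12.1.2 directs the expert to the AE list and not to those listings. A statistical analysis plan could add laboratory tables, but it could not put on the AE list events that sites were told not to report.

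A reader might infer more than the documents support:

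- *That marked laboratory abnormalities can never reach the review, or that none are captured.* Rows 3, 5 and 6 of the table show open routes, and Section 12.1.2's second kind of example is unaffected.
- *That values just short of a Section 5.4.1 criterion would be missed.* The haemoglobin figure there is one component of a composite haemolysis rule, not a criterion of its own. The transaminase item also allows stopping for any liver-test pattern that causes concern, and a separate item covers risk judged by the investigator or sponsor. Such values could therefore lead to discontinuation and be reported as DAEs.
- *That the absence of a data monitoring committee makes this worse.* OAE classification is a sponsor reporting step that such a committee would not perform.
- *That Section 7.3.3 sets the wrong AE threshold.* The documents show only that it does not fit Section 12.1.2. Changing what sites record would be a separate trade-off.

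**Conclusion.** Sections 7.3.3 and 12.1.2 conflict as written. An asymptomatic, non-serious abnormality in a protocol-mandated measurement that does not stop treatment cannot be classed as an OAE, although Section 12.1.2 names marked laboratory abnormality as its first example. Visit 5 findings are the clearest case, because the discontinuation condition is closed to them.

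The effect is confined to medical review and OAE reporting. Data collection, stopping criteria, listings and the efficacy analysis are untouched. The documents give no incidence for such abnormalities, so the number of patients affected cannot be estimated.

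The conclusion assumes that the reviewed list is the list of reported AEs, as Section 12.1.2 says, and that sites apply Section 7.3.3 literally. The broader AE definition in Section 7.3.1, which includes abnormal investigation results, might lead some sites to report more. That would make laboratory OAEs depend on local reading of the protocol. The conflict should be corrected, since a statement of no laboratory OAEs would otherwise be uninterpretable for this class of finding.

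**What to change.** Reconcile the two sections by amending Section 12.1.2. The OAE review should cover the AE list less SAEs and DAEs, plus the listed laboratory and vital-sign results from all visits and the recorded investigator ECG evaluations. Section 7.3.3 can stay as it is. The abbreviation list's pointer for the OAE definition should be corrected at the same time: it cites Section 12.2.4, but the text is in Section 12.1.2.

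The cost is one changed sentence and a short additional review by the same medical expert for about 40 patients, using listings that Section 13.2 already provides for. The limit is that results not held in the database (numeric QTc, unconjugated bilirubin and S-CPK-MB) would be covered only if the expert goes to source records, and the amended text should say whether that is intended.
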